^j Disease assessment will be performed on blood, bone marrow samples, and/or other tissue samples at these time-points. For Group 1 and Group 2, the screening disease assessment may be performed as part of SoC (prior to consent if it was already completed). For Group 1, pre-transplant testing of MRD should be performed locally by any testing methodology and results recorded in the eCRF. Post-transplant baseline MRD testing will be performed centrally, and results must be available prior to randomization. If any additional disease assessments, such as additional time points or additional testing (e.g., imaging for extramedullary disease), or visits occur due to clinical necessity, information will be recorded on eCRF. Includes central testing for MRD status for all samples collected as per SoC and as per standard institutional guidelines at other time points by methods outlined in protocol in Section 4.1 (samples stored for central confirmation at later date). If imaging is performed on a patient, the Sponsor may request imaging to be sent to a central vendor along with any disease assessment reports.

Disease assessment at Day 0 for Group 1 only (disease assessment does not need to be repeated if within 3 weeks of prior disease assessment and results can be pending prior to treatment).

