5.1. Patient Inclusion Criteria

All applicable inclusion and exclusion criteria must be met at Screening (up to 28 days before allogeneic HSCT for Group 1 patients, and prior to the start of manufacturing for Group 2 patients, or at the time of consideration for study) and at Baseline (re-assessment of eligibility within 14 days prior to group assignment for Group 1).

Patients are eligible to be included in the study only if all of the following criteria apply and the patient, in the judgement of the investigator, is an appropriate candidate for experimental therapy:

- 2. Eligible to receive donor-derived MT-401 following first allogeneic HSCT, are in ≤ third complete remission (CR3) prior to transplant (including matched sibling, matched unrelated donor with at least 6 of 8 HLA markers, or haploidentical with at least 5 of 10 HLA markers) as:
 - Adjuvant therapy for AML (**Group 1**) at 85-130 days post-HSCT defined as:
 - patients with CR_{MRD}- by central testing for purposes of randomization (if optional local MRD testing performed and results are positive, the patient will be moved to Group 2 subgroup D);
 - and are considered intermediate/high risk (e.g., pre-transplant MRD+, intermediate/adverse risk cytogenetics or received non-myeloablative or reduced intensity conditioning); or
 - Treatment for relapsed AML (first relapse post-HSCT) when disease occurs after transplant (Group 2) defined as
 - First relapse (MRD+ or frank relapse) post-HSCT
 - Patients in Group 1 who are randomized to Arm B (SoC) and experience first relapse (MRD⁺ or frank relapse) post-HSCT or experience relapse prior to randomization
 - Patients with frank relapse will enter into Subgroup C while patients with MRD⁺ disease will enter into Subgroup D
 - Safety Lead-in (Cohorts I and II) and Cohorts III-V defined as patients whose prior treatment course does not meet precise eligibility criteria but may still be approved upon review by the Sponsor as described above for Group 2 only

Note: Engraftment must be confirmed post-transplant (absolute neutrophil count $> 1000/\text{m}^3$ without granulocyte colony-stimulating factor for 7 days, donor chimerism $\ge 50\%$).

- 2. Are ≥18 years of age prior to administration of MT-401
- 3. Patients must have donor-derived cells available to make MT-401

Confidential Page 34 of 74

- 4. Karnofsky/Lansky score of ≥60
- 5. Life expectancy ≥ 12 weeks
- 6. Adequate blood, liver, and renal function

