8.1.1. Disease Assessment - Response Criteria in AML

The response criteria in AML (Döhner et al, 2017) are as follows in Table 6Relapse includes either hematologic and/or molecular relapse as defined in Table 6 at any disease assessment.

Confidential Page 43 of 74

Table 6. Response Criteria in AML

Category	Definition
CR without minimal residual disease $(CR_{MRD}$ -)	If studied pretreatment, CR with negativity for a genetic marker by quantitative reverse transcription polymerase chain reaction (RT-qPCR), or CR with negativity by multiparameter flow cytometry (MFC) and/or molecular testing
Complete remission (CR)	Bone marrow blasts <5%; a bsence of circulating blasts and blasts with Auer rods; a bsence of extramedullary disease; a bsolute neutrophil count \geq 1.0 x 10 $^9/L$ (1000/µL); platelet count \geq 100 x 10 $^9/L$ (100,000/µL) Note: MRD $^+$ or unknown
CR with incomplete recovery (CR _i)	All CR criteria except for residual neutropenia ($<1.0 \times 10^9/L [1000/\mu L]$) or thrombocytopenia ($<100 \times 10^9/L [100,000/\mu L]$)
Morphologic leukemia-free state (MLFS)	Bone marrow blasts <5%; absence of blasts with Auer rods; absence of extramedullary disease; no hematologic recovery required
Partial remission (PR)	All hematologic criteria of CR; decrease of bone marrow blast percentage to 5 to 25 percent; and decrease of pretreatment bone marrow blast percentage by at least 50 percent
Treatment failure	
Primary refractory disease	No CR or CR _i a fter 2 courses of intensive induction treatment; excluding patients with death in a plasia or death due to indeterminate cause
Death in a plasia	Deaths occurring ≥7 days following completion of initial treatment while cytopenic; with an aplastic or hypoplastic bone marrow obtained within 7 days of death, without evidence of persistent leukemia
Death from indeterminate cause	Deaths occurring before completion of therapy, or <7 days following its completion; or deaths occurring ≥7 days following completion of initial therapy with no blasts in the blood, but no bone marrow examination available
Response criteria fo	
Stable disease ^a	Absence of CR _{MRD} -, CR, CR _i , PR, MLFS; and criteria for PD not met

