Disease assessments will be performed by local and central laboratory facilities. Screening assessments for Group 1 patients can be a prior disease assessment completed within 45 days of screening as per SOC. For Group 1, pre-transplant testing of MRD should be performed locally

by any testing methodology and results recorded in eCRF. Post-transplant baseline MRD testing will be performed centrally and results must be available prior to randomization. MRD⁺ will be defined as CR (including normalization of counts) with detection in blood, bone marrow or any other tissues by flow cytometry and/or molecular testing (eg, PCR, next generation sequencing).

The study will evaluate safety and efficacy endpoints in post-HSCT patients after the infusion of MT-401 using standard methods of assessment (peripheral blood and bone marrow evaluation, positron-emission tomography [PET] scan, etc.). Response will be evaluated using the European LeukemiaNet (ELN) recommendations and repeated MRD assessment. Historical data will inform the clinical relevance of the magnitude and durability of response in Group 2 and will supplement data from the concurrently randomized control arm in Group 1 (Arm B). A synthetic control arm may also be identified for Group 2C. If created, the specifications of this control arm and analysis methods to be used will be documented in a separate statistical analysis plan.

The Data Monitoring Committee (DMC) will review data after the first 45 RFS events in Group 1 have been observed to assess safety and evaluate estimates of RFS for possible Group 1 enrollment expansion. Additionally, the sponsor will review safety and efficacy data in Group 2 after the first 10 patients per subgroup have progressed or had the opportunity to be followed for 6 months.

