6.4 Efficacy and Safety Variables

6.4.1 *Efficacy Variables*

6.4.1.1 *Disease Assessment – Response Criteria in AML*

Disease will be assessed by standard criteria at the time points listed in the schedule of assessments in Section 1.2.1 of the clinical study protocol. The ELN recommendations for AML (Döhner et al, 2017) are as follows in [Table 2](#).

Table 2. Response Criteria in AML

Category	Definition
CR without minimal residual disease (CR _{MRD-})	If studied pretreatment, CR with negativity for a genetic marker by quantitative reverse transcription polymerase chain reaction (RT-qPCR), or CR with negativity by MFC by multiparameter flow cytometry (MFC)
Complete remission (CR)	Bone marrow blasts <5%; absence of circulating blasts and blasts with Auer rods; absence of extramedullary disease; absolute neutrophil count $\geq 1.0 \times 10^9/L$ ($1000/\mu L$); platelet count $\geq 100 \times 10^9/L$ ($100,000/\mu L$) Note: MRD ⁺ or unknown
CR with incomplete recovery (CR _i)	All CR criteria except for residual neutropenia ($< 1.0 \times 10^9/L$ [$1000/\mu L$]) or thrombocytopenia ($< 100 \times 10^9/L$ [$100,000/\mu L$])
Morphologic leukemia-free state (MLFS)	Bone marrow blasts <5%; absence of blasts with Auer rods; absence of extramedullary disease; no hematologic recovery required
Partial remission (PR)	All hematologic criteria of CR; decrease of bone marrow blast percentage to 5 to 25 percent; and decrease of pretreatment bone marrow blast percentage by at least 50 percent
Treatment failure	
Primary refractory disease	No CR or CR _i after 2 courses of intensive induction treatment; excluding patients with death in aplasia or death due to indeterminate cause
Death in aplasia	Deaths occurring ≥ 7 days following completion of initial treatment while cytopenic; with an aplastic or hypoplastic bone marrow obtained within 7 days of death, without evidence of persistent leukemia
Death from indeterminate cause	Deaths occurring before completion of therapy, or < 7 days following its completion; or deaths occurring ≥ 7 days following completion of initial therapy with no blasts in the blood, but no bone marrow examination available
Response criteria for clinical trials only	
Stable disease ^a	Absence of CR _{MRD-} , CR, CR _i , PR, MLFS; and criteria for PD not met

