- CR: For Subgroup C, CR is defined as the proportion of patients who achieve a best response of CR_{MRD-} or CR using the ELN recommendations. For Subgroup D, CR rate is defined as the proportion of treated patients who achieve a best response of CR_{MRD-}. Best overall response (BOR) is defined as the best response designation recorded between the date of first dose and the date of objectively documented relapse per ELN recommendations or the date of subsequent therapy, whichever occurs first. For patients without documented relapse or subsequent therapy, all available response designations will contribute to the BOR assessment.
 - The incidence of converting MRD+ to MRD- was chosen as the primary endpoint for Subgroup D based on the following rational: (1) 2017 ELN recommendations (Döhner et al, 2017) introduced a new response category of CR MRD- recognizing MRD assessment provides a more reliable predictor of outcome than morphological assessment and MRD status has been consistently shown to be an independent prognostic marker for disease outcome (Short et al, 2020; Schuurhuis et al, 2018). (2) Given the nature of single arm design, a binary endpoint was considered a more appropriate primary endpoint than a time to event endpoint such as RFS or OS.
- DOCR: For Subgroup C, DOCR is defined as the time between the date of first documented response of CR_{MRD-} or CR to the date of the first documented relapse per ELN recommendations or death due to any cause, whichever occurs first. For Group 2 Subgroup D, duration of complete response is defined as the time between the date of first documented response of CR_{MRD-} to the date of the first documented relapse per ELN recommendations or death due to any cause, whichever occurs first. For patients who neither relapse nor die prior to analysis cutoff or the start of new anti-cancer therapy, DOCR will be censored on the date of their last evaluable disease assessment on or after the assessment of first documented CR and prior to analysis cutoff or start of new therapy.

6.4.1.3 *Secondary Efficacy Variables*

Safety Lead-in (Cohorts I and II) and Cohorts III-V:

- CR (Active disease patients): defined as above for Group 2
- DOCR (Active disease patients): defined as above for Group 2

Phase 2 Adjuvant (Group 1):

- OS: defined as the time between the date of randomization and the date of death. A patient who has not died will be censored on their last contact date (“last known alive date”).

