7.2 Analysis Populations

The analysis populations are defined as follows:

- All Treated Patients: Includes all patients who received at least one dose of MT-401 or were randomized to SOC.
- All Randomized Patients: Includes all patients in Group 1 who were randomized with final dose and manufacturing process and are MRD⁻ prior to randomization by central testing and local testing, if a local test was also performed. A patient randomized based on negative MRD result per central test but confirmed to be MRD⁺ will be excluded from Group 1 analysis.

When MRD testing occurs with different methodology (eg, flow cytometry and PCR), the patient is considered MRD⁺ if either test detects MRD. If adjudication occurs between central testing and local testing for the same type of testing (eg, flow by central testing and flow by local testing), the final adjudicated result will be taken into account for the confirmed MRD result. A patient confirmed to be MRD⁺ prior to randomization will be excluded from Group 1 and will be included in Group 2 analysis if treated with MT-401.

- Per-Protocol (PP) Population: Includes all treated patients, as defined above, who have no major protocol deviations. If there is <5% difference in the all randomized patient population and the PP population for Group 1, no analyses will be performed on the PP population.

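### Subgroup D: a patient in CR with discordant MRD assays fits both the CR, MRD-positive and the CR_MRD- wording, and no post-dose rule says which one counts for the primary endpoint

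*SAP*

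**What the plan says.** **Entry.** SAP 6.1 and Protocol 4.1 define MRD positivity as CR "with detection in blood, bone marrow or any other tissues by flow cytometry and/or molecular testing (eg, PCR, next generation sequencing"). One positive method in one tissue is enough. Protocol 5.1 sends these patients on: those with MRD-positive "disease will enter into Subgroup D".

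**Response.** SAP Table 2 (6.4.1.1) gives CR_MRD- two alternatives joined by an or: "CR with negativity for a genetic marker by quantitative reverse transcription polymerase chain reaction (RT-qPCR), or CR with negativity by MFC". Protocol Table 6 (8.1.1) keeps that structure but is wider: "or CR with negativity by multiparameter flow cytometry (MFC) and/or molecular testing". In both tables the plain CR row is annotated as MRD-positive or unknown.

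**Endpoint.** The Subgroup D rate is the proportion of treated patients with a best response of CR_MRD- (SAP 6.4.1.2; Protocol 9.3.3), and best overall response is the best designation recorded from first dose onward. SAP 6.4.1.2 states the intent: "The incidence of converting MRD+ to MRD- was chosen as the primary endpoint for Subgroup D".

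**Discordant methods.** The only rule is in SAP 7.2, where "the patient is considered MRD⁺ if either test detects MRD". It stands inside the definition of the All Randomized (Group 1) population and concerns status before randomization.

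**Specimens.** Protocol Table 1, footnote j: "Disease assessment will be performed on blood, bone marrow samples, and/or other tissue samples at these time-points".

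**The concern.** A positive on any one assay makes a patient MRD-positive, while a negative on one of two assays satisfies the CR_MRD- row. Neither document requires the assay or marker that was positive at baseline to be the one that turns negative. The qualifier about pretreatment study of the marker asks only that it was studied, not that it was positive and has cleared.

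Discordance is foreseeable under this plan. Protocol 5.1 moves a centrally negative patient to Subgroup D on a positive local test. SAP 7.2 anticipates flow and PCR disagreeing. SAP 7.4.6 plans a PCR summary only for those Subgroup D patients who had PCR detection at baseline, which implies that others qualified by another method.

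At stake is who counts as a responder on a primary endpoint in an open-label, single-arm subgroup read against historical rates. No concurrent control would absorb misclassified responders, and the duration endpoint starts from the same designation. A rule left open can also be settled after responses are known.

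**Working it through.** **1. The passages applied to one patient.** Take a patient in CR, PCR-positive and flow-negative at baseline, with the same results at Week 12.

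- General MRD-positive definition (SAP 6.1): met at both visits through PCR.
- CR row, noted MRD-positive or unknown: met at both visits.
- CR_MRD- row, flow-negativity alternative: met at both visits.
- Best overall response: picks the better post-dose designation, CR_MRD-, if it was recorded.
- SAP 7.2 either-positive rule: silent on Week 12.

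Two rows of one table fit the same sample, and nothing says which prevails.

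**2. Method lists.** MRD positivity allows flow, PCR and sequencing. SAP Table 2 judges response by RT-qPCR or flow only. Protocol Table 6 adds molecular testing. SAP 7.7 declares no change from the protocol, so the SAP omission is unexplained.

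**3. Reproducing the plan's decision rule.** Inputs: n = 30 per subgroup (SAP 7.6) and the one-sided exact 0.05 test in the footnote to SAP Table 3. The limit is the smallest r with P(X ≥ r | n = 30, p0) ≤ 0.05. For p0 = 20%, r = 11 with exact size 0.0256. Power is 0.811 at 43% and 0.907 at 47%, and the exact 95% interval at 43% is 25.2% to 62.3%. The table states 43% (25%, 62%) for 80% power and 47% for 90%. Of its 16 entries, 15 reproduce within 2 power points; the exception is 60% against 35%, with power 0.825. SAP 7.4.7.5 instead tests Group 2 CR at two-sided 0.05, which moves the limit to 12 of 30 (upper-tail size 0.0095). Both limits are shown below.

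**4. Size.** The documents give neither the share d of Subgroup D patients who are discordant at baseline nor a fixed Subgroup D benchmark. Both are assumed. Suppose every discordant patient stays in CR and is scored as a responder, and the rest respond at p = 20%. Then apparent rate = p + d(1 − p); for d = 10%, 0.20 + 0.10 × 0.80 = 0.28. Extra responders = 30 × d × (1 − p).

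| Assumed d | Apparent rate | Extra responders of 30 | P(X ≥ 11), one-sided 0.05 | P(X ≥ 12), two-sided 0.05 |
|---|---|---|---|---|
| 0% | 20% | 0 | 2.6% | 0.9% |
| 5% | 24% | 1.2 | 8.3% | 3.8% |
| 10% | 28% | 2.4 | 19.4% | 10.6% |
| 20% | 36% | 4.8 | 53.8% | 38.9% |
| 30% | 44% | 7.2 | 84.0% | 73.2% |

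With a 10% benchmark and a true rate of 10%, the limits are 7 and 8 of 30. For d = 10%, 20% and 30% the chances are 34%, 78% and 96% one-sided (2.6% at d = 0), and 20%, 63% and 92% two-sided (0.8% at d = 0).

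Each row is an upper bound for its d, because all discordant patients are scored leniently. If only half of a 10% discordant share were, the 5% row applies.

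**The case against.** The strongest reply is that a strict reading is available. The MRD-positive definition carries no time limit, so it can govern Week 12 as well as entry. With the note on the CR row, a patient still PCR-positive would be CR and not CR_MRD-, as the stated aim of conversion implies. The automatic responder appears only if the any-positive rule is used before dosing and the any-negative rule after. If the lenient rule were used at both times, a bridged patient would already be CR_MRD- before dosing, and SAP 7.6 would analyze that patient separately, outside the 60. This stands in part: a reader might infer that the plan deliberately sets opposite rules for entry and response, and the documents do not support that. But the strict reading is not written as a rule. The same sample still fits the CR_MRD- row, best overall response favors that row, and the bridging provision does not cover unbridged patients.

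Two further inferences go too far. One is that a patient positive in marrow would be cleared on blood alone. CR itself needs a marrow blast count, and detection in any tissue meets the MRD-positive definition. The other is that a patient who qualified by sequencing can never be judged by sequencing. That holds for SAP Table 2 only, since Protocol Table 6 includes molecular testing.

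Group 2 is also described as estimation without a formal power calculation, although SAP 7.4.7.5 does test CR at 0.05. The planned PCR-reduction summary (SAP 7.4.6) would show persistent PCR positivity, but it does not change who counts as a responder. A laboratory manual or review-committee charter, not available here, may hold a scoring rule; a primary-endpoint definition still belongs in the protocol and SAP.

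**Conclusion.** The concern holds as an unresolved conflict in a primary-endpoint definition. A Subgroup D patient in CR with discordant methods fits both descriptions at one visit, and neither document sets precedence after dosing. Read literally, the endpoint can count patients who never converted, against its stated purpose. SAP Table 2 is also narrower than both the MRD-positive definition and Protocol Table 6.

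The definitional gap follows from the text alone. Its size does not: it rests on an assumed discordant share, an illustrative 20% benchmark, and lenient scoring of every discordant patient. On those terms a true 20% rate could appear as up to 28%, 36% or 44%, with a false-positive chance of up to 19%, 54% or 84% one-sided, or 11%, 39% or 73% under the SAP's two-sided test. A reader might take these as predicted error rates; the documents give no basis for that.

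**What to change.** In SAP Table 2 and 6.4.1.2, and in Protocol Table 6 and 9.3.3:

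- State that for Subgroup D, CR_MRD- requires CR with no MRD detected by any method or in any tissue tested at that visit. This applies the plan's own any-positive rule (SAP 6.1 and 7.2) at every post-dose visit.
- State that a patient whose baseline-positive marker is still positive is scored CR, not CR_MRD-.
- Where the method positive at baseline was not repeated, flag the patient and, as a sensitivity analysis, show the rate with such patients counted as non-responders. Making this the primary rule could create non-responders, or require new testing, when a patient qualified on a local assay and is followed centrally.
- Make SAP Table 2 list the same methods as the MRD-positive definition and Protocol Table 6.

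Settle this before Subgroup D responses are tabulated for the Group 2 interim. The cost is wording in both documents, one sensitivity table, and a somewhat lower reported CR_MRD- rate. Because the rule uses whatever was tested at each visit, it adds no sampling.
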